## 8.1.2 Definition of secondary outcomes

### 8.1.2.1 Medical imaging specialists' diagnosis

The CXR radiologist, the LDCT radiologist and the LUS ultrasonographer assessed the probability of pneumonia using a three-point Likert scale

1. 'low'
2. 'intermediate'
3. 'high'

The diagnosis of pneumonia will be classified as follow

- positive (pneumonia) if the probability is rated as 'intermediate' or 'high'
- negative (pneumonia-free) if the probability is rated 'low'

cf. previous paragraph for actual positives and actual negatives definitions.

By defining the following elements:

**True Positives** are actual positives diagnosed with pneumonia by the imaging specialist

**False Positives** are actual positives diagnosed as pneumonia-free by the imaging specialist

**False negatives** are actual negatives diagnosed with pneumonia by the imaging specialist

**True negatives** are actual negatives diagnosed as pneumonia-free by the imaging specialist

**Diagnostic performance measures** (accuracy, sensitivity, specificity, PPV, NPV, PLR, NLR) will be evaluated for each **medical imaging specialist**:

- the CXR radiologist
- the LDCT radiologist
- the LUS ultrasonographer

### 8.1.2.2 Diagnostic outcomes

The outcomes to be analysed may consist of either

- (1) the response provided by the **physician in charge**, or
- (2) the response from the **study expert investigator** following the first round of the

**Delphi survey.** At that stage, the expert only has access to REDCap data — i.e., the examination results — but not the imaging series or the full patient record.

- **Unmasked imaging modalities in emergency.** Urgent need to unblind the examination in case of immediately life-threatening findings (yes/no) was collected for each exam (CXR / LDCT / LUS). See [Box2](#).
- **Alternative/concomitant diagnoses** provided by (2) the **study expert** following the 1st round of the Delphi survey. Experts were asked about:
  - **alternative** diagnosis in case of a *low* probability of pneumonia
  - **concomitant** diagnosis in case of an *intermediate* or *higher* probability of pneumonia.the experts could choose among
  - Cardiac Failure
  - Exacerbation COPD/emphysema/asthma
  - Acute bronchitis
  - Pulmonary malignancy
  - Interstitial lung disease
  - Pneumothorax
  - Other
- **Probability of aspiration pneumonia** provided by (2) the **study expert**. Experts were asked to rate the probability as low/intermediate/high in case of a *low* probability of pneumonia
- **Type of pneumonia** according to (2) the **study expert** (viral or bacterial). Experts were asked to provide the type of pneumonia in case of a *low* probability of pneumonia.
- **Additional imaging studies ordered during the acute setting** by (1) the **physician in charge**  
The following additional imaging performed by the physician in charge were collected. For each type of imaging, its number was also collected
  - Chest X Ray
  - Pulmonary CT scanner
  - Lung ultrasound by radiologist
  - Echocardiography by a cardiologist
- **Other procedures prescribed during the acute setting** by (1) the **physician in charge**
  - Non-invasive ventilation
  - Pleural puncture (“*thoracentesis*”, indicated in the one month visit *instrument*)

#### 8.1.2.3 Treatment outcome

- **Antibiotic free days** at day 30. The number of days of antibiotics during the first month was collected in REDCap (*antibiotic\_days\_firstmonth*). The number of antibiotic free days will be calculated as follow:

$$\text{Antibiotic free days} = 30 - \text{antibiotic\_days\_firstmonth}$$

For deceased patients, the number of antibiotic free days will be calculated as:

$$\text{Antibiotic free days} = \text{number of days alive} - \text{antibiotic\_days\_firstmonth}$$

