### 3.4 Timing of outcome assessments (timepoints)

Study periods	Timeline of patient enrolment/allocation, interventions and assessments						
	Screening	Randomisation	Discharge from ER	Discharge from the acute setting	Day 30	Day 90	Reference diagnosis
Visit	1	2	3	4	5	6	7
Time (hour, day)	hr0	hr2*	hr6*	dx	d30	d90	
Demographics	x						
Medical history	x						
Inclusion/exclusion criteria	x						
Physical examination	x						
Vital signs	x						
Laboratory tests	x			x			
CXR, LDCT, LUS		x					
Main diagnosis before ER discharge			x				x
Other diagnosis outcomes		x		x			x
Number of antibiotic free days					x		
Clinical, safety and cost outcomes			x		x		
Readmission and mortality					x	x	
QoL questionnaire			x		x	x	
Panel of experts							x

\*Approximately.  
CXR, chest x-ray; d, day; ER, emergency room; hr, hour; LDCT, low-dose CT; LUS, lung ultrasonography; QoL, quality of life.

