### 3.7 Timing of final analysis

All outcomes collected up to 90 days will be analysed after study completion and expert adjudication. Following the completion of data entry, data validation and cleaning will be performed. Data analysis will start after the database has been locked.

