#### 8.1.2.4 Clinical outcomes

- **Number of days requiring oxygen therapy** will be analysed for descriptive purposes only.
- **Length of stay (in the acute care setting)** will be calculated as the number of days between the emergency entry date (*emergencydate*) and the hospital discharge date (*hospital\_discharge\_date*)
  - A stay of 1 day corresponds to admission and discharge on the same calendar day.
  - A stay of 2 days corresponds to discharge on the day after admission, and so on.
- **Discharge after emergency** will be defined as a hospital stay of 1 day – that is, when the emergency entry date (*emergencydate*) and the hospital discharge date (*hospital\_discharge\_date*) fall on the same calendar day.
- **Transfer to the ICU/IMCU within 30 days** after the initial emergency admission/evaluation will be considered as having occurred if **either** of the following conditions is met:
  - The time between emergency entry date (*emergencydate*) and the hospital discharge date is  $\leq 30$  days **and** the discharge destination (*discharge\_place*) is ICU or IMCU; or
  - The 1-month follow-up visit reports a transfer to ICU (*transfer\_to\_icu*) or IMCU (*transfer\_imcu*), **and** the delay between the emergency entry date (*emergencydate*) and the ICU/IMCU admission date (*icu\_transfer\_date* or *imcu\_transfer\_date*) is  $\leq 30$  days
- **Transfer to a rehabilitation unit within 90 days** after the initial emergency admission/evaluation will be considered as having occurred if **either** of the following conditions is met:
  - The discharge destination (*discharge\_place*) is rehabilitation and the delay between *emergencydate* and *hospital\_discharge\_date* is  $\leq 90$  days; or
  - A transfer to rehabilitation (*rehabilitation*) with a corresponding admission date (*rehabilitation\_date*)  $\leq 90$  days after *emergencydate* is reported at the 1- or 3-month follow-up.
- **Transfer to a long-term care facility (LTCF) within 90 days** after the initial emergency admission/evaluation will be considered as having occurred if **either** of the following conditions is met:

- The discharge destination (*discharge\_place*) is LTCF and the delay between *emergencydate* and *hospital\_discharge\_date* is  $\leq$  90 days; or
- A transfer to LTCF (*transfer\_ltcf*) with a corresponding admission date (*ltcf\_transfert\_date*)  $\leq$  90 days after *emergencydate* is reported at the 1- or 3-month follow-up.

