- **All-cause mortality within 30 days** will be defined as a death date (*death\_date* or *deathdate*) occurring within **30 days** of the emergency entry date (*emergencydate*)

- **All-cause mortality within 90 days** will be defined as a death date (*death\_date* or *deathdate*) occurring within **90 days** of the emergency entry date (*emergencydate*)

- **In-hospital mortality** will be defined as a death occurring on or before the hospital discharge date (*hospital\_discharge\_date*), based on the recorded death date (*death\_date* or *deathdate*)

- **All-cause readmission within 90 days** after initial emergency admission/evaluation will be defined as a readmission date (*readmission\_date*) occurring within **90 days** of the emergency entry date (*emergencydate*)

- **Quality-of-life at 30 days and 90 days** (*eq5d\_score*)

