#### 8.2.3.3 Treatment outcome

Number of antibiotic free days at day 30 will be compared between the three arms using a linear regression model adjusted on centre with a bootstrap method for 95%CI. P values will be computed by inverting the corresponding confidence interval (Thulin 2024: modern statistics with R).

- a subgroup analysis excluding exacerbation of COPD, where the need for antibiotic therapy is still debated, will be performed.

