#### 8.2.4 Assessment of statistical assumptions

The Cochran-Mantel-Haenszel method requires that stratification by centre is appropriate, with sufficient patient numbers per centre to provide reliable estimates. Since the study will include approximately 500 patients distributed across three centres, it is expected that the sample size per centre will be large enough to satisfy this requirement and provide stable stratified estimates.

Regression models (linear or logistic) assume independence of observations; homoscedasticity and normality of residuals for linear models; and linearity of the logit for logistic regression (when continuous predictors are included). Survival analyses assume non-informative censoring and proportional hazards over time. For linear models, the assumptions will be checked graphically (scatter plots, scale-location plots, residual-versus-fitted values plot). The proportionality of hazards will be graphically checked with the log-minus-log plot and regression coefficients based on categorizations of the continuous variable. The proportionality of log-odds will be checked with the regression coefficients of categorized variables. If significant violations of key assumptions are detected (e.g., non-normality of residuals, heteroscedasticity, or sparse data in logistic models), alternative methods (e.g., data categorization, exact methods, or non-parametric approaches) or sensitivity analyses will be considered and documented.

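### The antibiotic-free-days formula for deceased patients has no day-30 limit, so a death on days 31 to 90 scores 1 to 60 days too high if the rule is coded as written (secondary outcome only)

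*SAP*

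**What the plan says.** SAP 8.1.2.3 introduces the outcome as antibiotic-free days "at day 30. The number of days of antibiotics during the first month was collected in REDCap" and scores patients as 30 − antibiotic_days_firstmonth. It continues: "For deceased patients, the number of antibiotic free days will be calculated as" number of days alive − antibiotic_days_firstmonth. The second formula carries no time qualifier and no cap, and the SAP does not define how days alive are counted.

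Four other places bear on the point:

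- SAP 8.1.2.4 defines "All-cause mortality within 90 days" from a recorded death date, so deaths after day 30 are in the database.
- SAP 3.7 says "All outcomes collected up to 90 days will be analysed after study completion and expert adjudication", so those dates will be available when the variable is derived.
- SAP 3.4 lists "Number of antibiotic free days" in the schedule at day 30 only.
- SAP 8.2.3.3 states the analysis: "Number of antibiotic free days at day 30 will be compared between the three arms using a linear regression model adjusted on centre", with bootstrap intervals. It repeats the day-30 label but adds no restriction.

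The protocol offers no fallback formula. It names the outcome in section 3.2, and in section 5.1 plans a different analysis: cumulative incidence over 30 days with death as a competing event.

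**The concern.** The two formulas use different horizons. For patients not recorded as deceased, the minuend is fixed at 30. For anyone recorded as deceased it is the whole survival time, which can reach 90 days, while the antibiotic days subtracted still cover only the first month. A patient alive on day 30 who dies later therefore gets credit for days outside the outcome window. Two patients with identical first-month histories receive different scores because of something that happened after that month.

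This is the only treatment outcome the SAP lists, and the arms are compared on means, so a few extreme values act directly on the estimate. The repeat analysis without COPD exacerbations would inherit them. The error runs in an awkward direction: late deaths look like antibiotic sparing.

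**Working it through.** The documents give no numeric figure for this outcome, so there is nothing to reproduce. The check is arithmetic on the two printed formulas.

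**Inputs.** a = antibiotic_days_firstmonth; d = death date minus emergencydate; horizon 30 days (SAP 8.1.2.3); death dates to day 90 (SAP 8.1.2.4); planned arm size 165 (SAP 3.5).

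**Excess for one patient.** Score as written: d − a. Score limited to day 30: min(30, d) − a. The excess is d − min(30, d), which is 0 for d ≤ 30 and d − 30 for d from 31 to 90, whatever the value of a.

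| Death on day | As written, a = 7 | Limited to day 30 | Excess |
|---|---|---|---|
| 20 | 13 | 13 | 0 |
| 31 | 24 | 23 | 1 |
| 60 | 53 | 23 | 30 |
| 75 | 68 | 23 | 45 |
| 90 | 83 | 23 | 60 |

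SAP 8.1.2.4 counts length of stay inclusively: "A stay of 1 day corresponds to admission and discharge on the same calendar day". If days alive were counted that way, each late-death excess would be one day larger (2 to 61), and a death on day 30 itself would score 1 day too high.

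**Shift in an arm mean from one late death** (excess / 165):

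- day 60: 30/165 = 0.18 day (inclusive count 31/165 = 0.19)
- day 90: 60/165 = 0.36 day (inclusive count 61/165 = 0.37)

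**Variance added by one late death**, if its excess is unrelated to antibiotic use: x² × (1/165) × (164/165).

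- day 60: 900 × 164/165² = 5.4 days²
- day 90: 3600 × 164/165² = 21.7 days²

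**Illustration with assumed inputs.** The documents give no late mortality, timing of late deaths or outcome SD. Assume deaths spread evenly over days 31 to 90. The mean excess is then (1 + … + 60)/60 = 30.5 days and the mean squared excess is 1230.2.

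- *Same late mortality q and timing in all arms.* The expected between-arm difference is zero, and the cost is precision. Added variance is 1230.2q − (30.5q)²: 12.2 at q = 1% and 36.1 at q = 3%. The approximate 95% half-width for two arms is 1.96 × √(2 × (SD² + added)/165). At SD 7 it goes from 1.51 to 1.69 (1%) or 1.99 (3%). At SD 5 it goes from 1.08 to 1.32 or 1.69; at SD 10, from 2.16 to 2.29 or 2.52. This normal two-arm formula only approximates the planned three-arm model with bootstrap intervals.
- *Imaging arm truly changes late mortality.* The bias is 30.5 × 0.01 = 0.3 day per percentage point of difference. It would be 0.16 if deaths fell evenly on days 31 to 60 (mean excess 15.5), and 0.46 if on days 61 to 90 (mean excess 45.5).

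**The case against.** The best defence is that the context supplies the limit. The outcome is labelled as a day-30 measure in both documents, the schedule places it at day 30 only, and subtracting a first-month variable makes sense only over a first-month window. Read so, the second rule means patients dead by day 30, and an antibiotic-free count of 83 at day 30 is absurd on its face. SAP 8.2.4 also provides a safety net: "For linear models, the assumptions will be checked graphically (scatter plots, scale-location plots, residual-versus-fitted values plot" are named, and a value of 53 or 83 would stand out.

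The argument from intent stands: a limit was probably meant, and a programmer who applies it avoids the late-death error. It does not change the printed rule. The neighbouring definitions of ICU transfer, rehabilitation, mortality and readmission each state their 30- or 90-day window, and this one does not. Plots may expose the values, but the remedies SAP 8.2.4 offers are other methods or sensitivity analyses, not a corrected derivation. Repairing the rule after seeing outliers would be a data-driven change to an outcome the SAP means to fix in advance.

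Two stronger readings are tempting and are not supported:

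- A reader might infer that any imbalance in late deaths between arms biases the comparison. Under randomisation, a chance imbalance in their number or timing is random error, already reflected in the inflated variance. Nor must number and timing both match for the effect to cancel, since the two can offset each other. Nothing in the documents shows that the imaging arm changes late mortality.
- A reader might infer from the protocol's 1-month visit window (−2/+10 days) that the antibiotic count runs to the visit date. That is a window for the visit. SAP 8.1.2.3 describes the variable as covering the first month, and the CRF wording is not available here to show otherwise.

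**Conclusion.** The point holds as a defect in the written rule, and it should be fixed. Applied exactly, SAP 8.1.2.3 gives every death on day d from 31 to 90 an excess of d − 30 days by plain date difference (one more if the entry day is day 1), and it can yield values above 30 on a 30-day scale. That rests on the printed formulas alone. The single-death shifts of 0.18 and 0.36 day need only the planned 165 per arm; the added variances also assume that late death is unrelated to antibiotic use.

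The effect on the arm comparison is conditional. It is systematic only if the imaging arm alters the rate or timing of late death. Otherwise it is lost precision, whose size depends on late mortality and an SD that the documents do not give. The defect is confined to this secondary outcome and its COPD-excluded repeat. The primary accuracy analysis is untouched, and no late-death error arises if the probable intent is programmed.

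**What to change.** Replace the two formulas in SAP 8.1.2.3 with one for all patients: antibiotic-free days = min(30, days alive from emergencydate) − antibiotic_days_firstmonth. Restricting the deceased formula to deaths within 30 days does the same under plain date difference. The min form is safer because it also holds a day-30 death at 30 under an inclusive count.

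State that days alive are counted on the same basis as antibiotic_days_firstmonth, for instance with the entry day as day 1 as already done for length of stay. Add a range check that sends any value outside 0 to 30 for query.

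The cost is one or two sentences, one line of code and the check. No new data are needed, and deaths before day 30 keep the score the present rule gives under the same counting basis. The change should be made before the variable is derived.

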#### 8.1.2.4 Clinical outcomes

- **Number of days requiring oxygen therapy** will be analysed for descriptive purposes only.
- **Length of stay (in the acute care setting)** will be calculated as the number of days between the emergency entry date (*emergencydate*) and the hospital discharge date (*hospital\_discharge\_date*)
  - A stay of 1 day corresponds to admission and discharge on the same calendar day.
  - A stay of 2 days corresponds to discharge on the day after admission, and so on.
- **Discharge after emergency** will be defined as a hospital stay of 1 day – that is, when the emergency entry date (*emergencydate*) and the hospital discharge date (*hospital\_discharge\_date*) fall on the same calendar day.
- **Transfer to the ICU/IMCU within 30 days** after the initial emergency admission/evaluation will be considered as having occurred if **either** of the following conditions is met:
  - The time between emergency entry date (*emergencydate*) and the hospital discharge date is  $\leq 30$  days **and** the discharge destination (*discharge\_place*) is ICU or IMCU; or
  - The 1-month follow-up visit reports a transfer to ICU (*transfer\_to\_icu*) or IMCU (*transfer\_imcu*), **and** the delay between the emergency entry date (*emergencydate*) and the ICU/IMCU admission date (*icu\_transfer\_date* or *imcu\_transfer\_date*) is  $\leq 30$  days
- **Transfer to a rehabilitation unit within 90 days** after the initial emergency admission/evaluation will be considered as having occurred if **either** of the following conditions is met:
  - The discharge destination (*discharge\_place*) is rehabilitation and the delay between *emergencydate* and *hospital\_discharge\_date* is  $\leq 90$  days; or
  - A transfer to rehabilitation (*rehabilitation*) with a corresponding admission date (*rehabilitation\_date*)  $\leq 90$  days after *emergencydate* is reported at the 1- or 3-month follow-up.
- **Transfer to a long-term care facility (LTCF) within 90 days** after the initial emergency admission/evaluation will be considered as having occurred if **either** of the following conditions is met:

- The discharge destination (*discharge\_place*) is LTCF and the delay between *emergencydate* and *hospital\_discharge\_date* is  $\leq$  90 days; or
- A transfer to LTCF (*transfer\_ltcf*) with a corresponding admission date (*ltcf\_transfert\_date*)  $\leq$  90 days after *emergencydate* is reported at the 1- or 3-month follow-up.

- **All-cause mortality within 30 days** will be defined as a death date (*death\_date* or *deathdate*) occurring within **30 days** of the emergency entry date (*emergencydate*)

- **All-cause mortality within 90 days** will be defined as a death date (*death\_date* or *deathdate*) occurring within **90 days** of the emergency entry date (*emergencydate*)

- **In-hospital mortality** will be defined as a death occurring on or before the hospital discharge date (*hospital\_discharge\_date*), based on the recorded death date (*death\_date* or *deathdate*)

- **All-cause readmission within 90 days** after initial emergency admission/evaluation will be defined as a readmission date (*readmission\_date*) occurring within **90 days** of the emergency entry date (*emergencydate*)

- **Quality-of-life at 30 days and 90 days** (*eq5d\_score*)

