Background and Rationale	
Principal study: OCTOPLUS
 
Pneumonia is one of the leading causes of morbidity and mortality from infection in elderly patients, and is one of the first causes of antimicrobial therapy prescription. Its diagnosis is challenging, particularly in elderly patients, because of the lack of sensitivity and specificity of clinical signs and symptoms and because of the high incidence of differential diagnoses. Limitation of chest X-Ray (CXR) for this diagnosis have been abundantly documented. Hence, clinical studies are needed to improve diagnosis of pneumonia, leading to better management of the patients and more appropriate antimicrobial therapy prescription.
 
We showed in a previous study that low-dose CT scan (LDCT) changed the probability of pneumonia in 45% of elderly patients (>65 years, median age 84 years) suspected of pneumonia according to clinical presentation and CXR (Prendki, Eur Resp J 2018). LDCT mostly helped the clinician to exclude a diagnosis of pneumonia. Another study showed a similar impact of CT in adult patients (>18 years, median age 65 years) consulting in the emergency department (ED) for a suspicion of pneumonia (Claessens, Am J Respir Crit Care Med 2015). Hence, CT-scan could contribute to a more accurate diagnosis of pneumonia in the emergency department setting. However, availability, costs, and associated irradiation are significant issues.
 
Lung ultrasonography (LUS) is a promising diagnostic tool for the detection of pulmonary infiltrates, with a reported accuracy outperforming CXR (Nazerian, Am J Emerg Med 2015). As it is readily available at the bedside, use of ultrasonography by non-specialists in the emergency room has significantly increased. However, published studies have mainly been conducted by team experts in LUS, and generalizability of their results to less specialized settings is unwarranted.
 
Finally, only a randomized-controlled trial (RCT) may establish if one diagnostic strategy leads to better or equivalent clinical

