#### 8.2.3.4 Clinical outcomes

- **All-cause mortality at 30 days** will be
  - estimated by arm using the Kaplan-Meier method
  - compared between arms through pairwise comparisons using a log-rank test stratified by centre (three pairwise tests will be performed)
  - and the complementary log-log transformation will be applied to calculate the 95% confidence intervals for the 30-day survival estimates
- **All-cause mortality at 30 days** will be described only
- **In-hospital mortality**
  - will be described by arm as count and percentages
  - will be compared between arms using a logistic regression model adjusted on centre. Odds ratio will be reported with 95% confidence intervals
- Number of patients hospitalised after emergency and number of patients discharged after emergency will be described by arm as count and percentages
- **Length of hospital stay**
  - Will be analysed **among all randomized patients, and repeated among hospitalized patients only** (excluding those discharged after emergency department presentation)
  - Will be compared between arms using a linear regression model adjusted on centre with a bootstrap method for 95%CI.
  - Pvalues will be computed by inverting the corresponding confidence interval (Thulin 2024: modern statistics with R).
- **Unplanned transfer to the ICU/IMCU within 30 days after initial admission/evaluation**
  - Will be analysed **among all randomized patients, and repeated among hospitalized patients only** (excluding those discharged after emergency department presentation)
  - Will be described by arm as count and percentages
  - Will be compared between arms using a logistic regression model adjusted on centre. Odds ratio will be reported with 95% confidence intervals.
- The following outcomes will be described by arm as count and percentages **in patients discharge alive**. Those outcomes will not be compared between arms:
  - **Admission to rehabilitation through 3 months in patients discharge alive**
  - **Transfer to LTCF through 3 months in patients discharge alive**
  - **All-cause readmission to acute care setting in patients discharge alive**
  -
- The **quality of life 30 days and 90 days** will be described by arm as median and IQR **in patients discharge alive**. Quality of life will not be compared between arms

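### The hospitalised-only repeats rest on a same-date rule that can class ICU/IMCU transfers as ED discharges, and they compare arms in a subset formed after the allocated image is seen

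*SAP*

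**What the plan says.** SAP 8.1.2.4 defines discharge after emergency as a one-day stay, meaning that emergencydate and hospital_discharge_date "fall on the same calendar day". The counting rule is explicit: "A stay of 1 day corresponds to admission and discharge on the same calendar day". Clock time, destination and vital status play no part.

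The same section gives two routes to a 30-day ICU/IMCU event. The first, ending "is ICU or IMCU; or", relies on discharge_place at the hospital discharge date, so ICU and IMCU are valid discharge destinations. The baseline table in 8.2.1 also lists both under place of discharge. In-hospital mortality "will be defined as a death occurring on or before the hospital discharge date".

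SAP 8.2.3.4 analyses length of stay and ICU/IMCU transfer "among all randomized patients, and repeated among hospitalized patients only", the latter "excluding those discharged after emergency department presentation". Length of stay "Will be compared between arms using a linear regression model adjusted on centre with a bootstrap method for 95%CI", with p values. ICU/IMCU transfer is compared by centre-adjusted logistic regression, reported as odds ratios with confidence intervals. Numbers hospitalised and numbers discharged after emergency are tabulated by arm.

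Protocol 5.1 plans no hospitalised-only comparison, and SAP section 9 does not list one as an addition.

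**The concern.** Two separate problems meet in one subset.

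**The label.** Equal dates do not identify patients who left the ED for home. The rule takes in a patient moved to ICU or IMCU on the arrival date, who is an event for one of the two outcomes being repeated. It misses a patient who leaves the ED after the date has changed. The by-arm count of hospitalised and discharged patients has the same fault, and hospital admission is a listed clinical outcome in SAP 3.3.2.

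**The conditioning.** The clinician assesses the patient with the allocated image before the patient leaves the ED (protocol 4.3, SAP 3.1), so admission or discharge follows randomisation and may depend on arm. Comparing arms among admitted patients then compares groups that randomisation did not form. If one strategy sends more low-risk patients home, its remaining inpatients have longer average stays and a higher ICU proportion with no harm done. Unplanned ICU transfer is a protocol safety outcome, so a spurious contrast would matter to readers.

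**Working it through.** **1. The date rule applied to example patients** (stay = difference in dates + 1)

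| Patient | Stay | Label under 8.1.2.4 | Actual course |
|---|---|---|---|
| Home from ED, 10:00 to 16:00 | 1 | discharged | discharged |
| Arrives 17:30, home from ED 00:30 | 2 | hospitalised | discharged |
| To ICU same day, discharge_place = ICU | 1 | discharged | ICU transfer |
| Dies in ED on arrival date, discharge date filled in | 1 | discharged | death |
| Ward stay, six dates later | 7 | hospitalised | hospitalised |

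The ICU patient is an event in the all-randomised analysis and absent from the hospitalised-only one.

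**2. Effect of lost events.** Assume 132 hospitalised and 8 ICU events per arm, so 124 non-events. Removing k same-day events from one arm gives OR = [(8 − k)/124] / [8/124] = (8 − k)/8. For k = 1, 2 and 4 this is 0.88, 0.75 and 0.50, where the true value is 1.00.

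**3. Effect of conditioning.** The plan states no figure on this point. The only documented input is the target of 165 per arm (SAP 3.5: 150 × 1.10 = 165). Everything else here is assumed. Let a_C and a_L be the proportions admitted under CXR and LDCT, with a_C > a_L. Patients admitted under either strategy stay L days, patients admitted only under CXR stay m days, and an ED discharge counts as 1 day. Then, for LDCT minus CXR:

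- hospitalised-only difference = (a_C − a_L)(L − m)/a_C
- all-randomised difference = (a_C − a_L)(1 − m)

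The signs are opposite whenever 1 < m < L.

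Example: a_C = 0.90, a_L = 0.80, L = 10, m = 5.

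- All randomised, CXR: 0.8×10 + 0.1×5 + 0.1×1 = 8.6 days
- All randomised, LDCT: 0.8×10 + 0.2×1 = 8.2 days
- Hospitalised only, CXR: (0.8×10 + 0.1×5)/0.9 = 9.4 days
- Hospitalised only, LDCT: 10.0 days
- ICU, 16 events per arm: 16/148.5 = 10.8% v 16/132 = 12.1%; OR = (16/116)/(16/132.5) = 1.14

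Range, with L = 9, m from 3 to 5 and 8 ICU events per arm:

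| Admission CXR v LDCT | Hospitalised-only difference (days) | All-randomised difference (days) | Hospitalised-only ICU OR |
|---|---|---|---|
| 90% v 85% | +0.2 to +0.3 | −0.2 to −0.1 | 1.06 |
| 85% v 75% | +0.5 to +0.7 | −0.4 to −0.2 | 1.14 |
| 80% v 65% | +0.8 to +1.1 | −0.6 to −0.3 | 1.25 |

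With an assumed SD of 6 days and a simple two-sample comparison of means, the chance of a significant hospitalised-only difference in stay runs from about 5% to 30% across these scenarios.

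**The case against.** The hospitalised-only results are repeats of secondary outcomes beside an all-randomised analysis. A reader might infer that the rule deletes early ICU events from the trial's ICU outcome. It does not: they remain in the all-randomised comparison. The by-arm admission counts would also let a reader see differential admission, subject to the same mislabelling. All of this stands.

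A reader might also take it as settled that ED deaths are labelled as discharges. The in-hospital mortality definition implies that deaths carry a hospital discharge date but does not say so, and the listed discharge places include no death category. If the field is blank for deaths, those patients cannot be classified at all.

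Mislabelled cases should be uncommon. Patients needing immediate ICU admission are excluded. Recruitment is at triage in working hours (protocol 4.2), and SAP 3.4 puts ER discharge at about hour 6. A transfer reported at the 1-month visit, with a later hospital discharge date, is kept in the subset. This limits the frequency but does not repair the definition.

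Finally, a reader might infer that LDCT will look harmful. The synopsis does say "LDCT mostly helped the clinician to exclude a diagnosis of pneumonia", but that is about diagnosis, not about sending patients home, and protocol section 2 describes that cohort as hospitalised patients. Alternative diagnoses such as cardiac failure may also need admission. An arm effect on admission is plausible but undocumented. With 16 events per arm, the odds ratio of 1.14 has an approximate 95% interval of 0.55 to 2.4, so the test alone would not show harm.

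**Conclusion.** The point holds within limits. The label is wrong by construction for a patient coded to ICU/IMCU on the arrival date and for a patient sent home from the ED on the next date. It is wrong for same-day deaths only if the discharge date is filled in for them. The number affected is unknown and probably small, though at 8 ICU events per arm even one or two losses in one arm would be visible.

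The conditioning is the more general weakness. Under the assumed admission gaps of 5 to 15 percentage points, the hospitalised-only difference in stay is 0.2 to 1.1 days in the opposite direction to the all-randomised one, and the ICU odds ratio is 1.06 to 1.25 with equal event counts. These sizes depend on admission rates, stays and event counts that the documents do not give. With equal admission rates and the same kinds of patient admitted in each arm, the selection would cause no distortion.

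The primary outcome and the all-randomised comparisons are unaffected. The SAP already follows the safer practice for another post-randomisation subset: in 8.2.3.4, outcomes in patients discharged alive are described and not compared between arms.

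**What to change.** - **SAP 8.1.2.4:** add to the date rule that a patient with a same-day death, or with discharge_place of ICU or IMCU, is never classed as discharged after emergency. State what hospital_discharge_date contains for deaths.
- **Next-date exits:** use recorded ED disposition or exit time if either was collected. The documents do not show that it was. If not, state the limitation.
- **SAP 8.2.3.4:** keep between-arm inference on length of stay and ICU/IMCU transfer for all randomised patients only. Report hospitalised-only results by arm descriptively, beside the corrected admission counts.
- **SAP section 9:** list the hospitalised-only analyses as additions to the protocol.

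The cost is SAP wording, one recoded variable built from fields the SAP already uses, and the loss of up to six supplementary comparisons (two outcomes × the three pairwise contrasts in 8.2.3). The SAP states that it was finalised before analysis began, so the change can still be prespecified if analysis has not started.
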